Appendix 2. Bayley Infant Neurodevelopmental Screener	36
Appendix 3. Bzoch-League Receptive-Expressive Emergent Language Test (3 rd Edition) (REEL-3)	38
Appendix 4. Guidance on Reporting Nonserious Adverse Events for A4091065	44

PROTOCOL SUMMARY

This is a multicenter, prospective, cohort study with enhanced physical and neurodevelopmental surveillance to characterize the neurological outcomes related to the development of infants up to the age of 15 months, who were exposed to tanezumab, placebo or comparator via maternal exposure at conception or in-utero in any tanezumab clinical study (A4091056, A4091057, A4091058, A4091059, A4091061, A4091063) at any investigational site. The post-natal monitoring will include assessments at birth (0-2 months), approximately 8 months and approximately 15 months of age and up to a maximum of 36 months of age as needed.

SCHEDE OF ACTIVITIES

The Schedule of Activities table provides an overview of the protocol visit and procedures. Refer to Study Procedures ([Section 6](#)) and Assessments ([Section 7](#)) sections of the protocol for detailed information on each procedure and assessment required for compliance with the protocol.

The investigator may schedule visits (unplanned visits) in addition to those listed on the schedule of activities, in order to conduct evaluations or assessments required to protect the well-being of the subject.

Protocol Activity	Screen	0-2 Months	8 Months	15 Months/ET ^{c,d}
		Visit 1	Visit 2	Visit 3
Informed consent	X			
History & Physical Examination				
Occipital-frontal head circumference		X	X	X
Length		X	X	X
Weight		X	X	X
Vital Signs		X	X	X
Post-birth age (weeks)		X	X	X
Neurological Examination		X	X	X
Developmental Assessments	BINS ^a REEL-3 ^b		X	X

- a. Bayley Infant Neurodevelopmental Screener. (BINS).
- b. Bzoch-League Receptive Expressive Emergent Language Test, third edition (REEL-3).
- c. End of Treatment (ET)/Follow up visit: The need for further physical, neurological or developmental evaluations will be determined at the 15 month visit by the pediatrician, pediatric neurologist or a psychologist.
- d. Post-study subject interview (if applicable): The need for additional post-study follow up visits will be determined subsequent to the Visit 3 (15 month) visit and may extend to a maximum of 36 months as needed (eg, should a physical or neurodevelopmental delay be observed to be not within the range of normal development by the evaluating pediatrician, pediatric neurologist, or psychologist, an additional interview may be conducted up to 36 months of age).

1. INTRODUCTION

1.1. Mechanism of Action/Indication

Tanezumab (PF-04383119, formerly RN624) is under development for the relief of signs and symptoms of osteoarthritis (OA), and management of moderate to severe chronic pain in conditions such as chronic low back pain (CLBP), and cancer pain due to bone metastasis.

1.2. Background and Rationale

1.2.1. Description of Investigational Product

Tanezumab is a humanized immunoglobulin G Type 2 (IgG2) monoclonal antibody, derived from a murine precursor by grafting the murine complementarity determining regions onto a human antibody framework, followed by extensive site-directed mutagenesis using proprietary technology to improve binding affinity and specificity. A mutation was performed in the Fc portion of the antibody to decrease its ability to activate complement or to support antibody dependent cell-mediated cytotoxicity.

Tanezumab is highly potent in sequestering Nerve Growth Factor (NGF) and preventing interaction with its receptors. Tanezumab and/or its murine precursor have been shown to be an effective analgesic in nonclinical animal models of pathological pain including arthritis, cancer pain, and post-surgical pain models.

The administration of a monoclonal antibody against human NGF, such as tanezumab, offers the potential to provide a novel, effective treatment of pain without the adverse effects or limited efficacy of currently available therapies.

1.2.2. Role of Nerve Growth Factor

During mammalian development, NGF is required for the survival and growth of several populations of neurons. However, NGF is not required for neuronal survival in adulthood. The role of NGF in the adult mammal appears to principally be as a modulator of nociceptive neuronal activity. Thus, NGF plays an important role in modulation of the pain response.^{1,2}

Anti-NGF antibodies were widely used to study the function of NGF from 1970 to about 1990, before the other members of the neurotrophic factor (NTF) family were discovered. Polyclonal antisera generated against NGF purified from mouse submaxillary gland were generally used in these studies.

Studies investigating the potential role of NGF in pre- and post-natal development of rodents by using direct injections of polyclonal antisera, the generation of female rodents autoimmune to their own NGF, and genetic knockouts of the NGF gene, have suggested that NGF is important for the proper embryonic development of sympathetic neurons, a subset of peripheral primary afferent neurons and perhaps for a small population of cholinergic neurons of the basal forebrain in rodents.^{3,4} The conclusions from these studies need to be interpreted with caution due to the limitations of the methods used and the knowledge base available at the time they were performed. First, the antisera bind to many different sites on NGF and are immunologically active, thereby potentially mediating toxic effects not due to

NGF deprivation per se. Second, since the vast majority of these studies took place before it was known that NGF is one of a closely related family of proteins, it is likely that many of the sera used in these studies cross react to those other members and hence some of the effects seen may be due to deprivation of molecules other than NGF. Tanezumab is specific for NGF, but is not expected to completely block all NGF.^{5,6}

Evidence available in the literature describes differences in transfer across the placenta into the embryo for IgG subclasses with transfer being greater for IgG1 and lower for IgG2. Unlike most therapeutic antibodies, tanezumab belongs to the IgG2 subclass rather than the more frequently employed IgG1 subclass. Organogenesis in humans is complete by gestation Day 56, and since IgG2 placental transfer is minimal during this period and the recommended human dosing interval for tanezumab is every 8 weeks (about every 56 days) the likelihood of significant embryonic exposure to a therapeutic antibody during this period is low.⁷

An analysis of the predicted tanezumab exposure in female partners via semen from male subjects was conducted and confirmed that tanezumab exposure via semen does not result in biologically relevant exposure to the fetus. The margin between partner exposure and the Minimum Anticipated Biological Effect Level (MABEL) is greater than 300-fold using very conservative estimates.⁸ The lack of genotoxic risk and lack of tanezumab-related effects on reproductive endpoints in non-human primates further supports no need for contraceptive requirements for men in any clinical studies of tanezumab or a need to monitor children of male subjects in tanezumab studies.

1.2.3. Safety of Tanezumab During Pregnancy and Study Rationale

As of February 2015, a total of 32 clinical studies involving over 11,000 subjects have been conducted (refer to Tanezumab Investigator Brochure, Feb 2015). Tanezumab is currently being studied as a treatment for osteoarthritis chronic lower back and cancer pain in an ongoing Phase 3 development program in approximately 6900 additional subjects to evaluate the efficacy and safety of tanezumab administered subcutaneously (SC). Additional subject populations may be considered in the future as part of the overall development plan for tanezumab.

Based on the mechanism of action of tanezumab, there could be a potential neurological developmental risk to a fetus, but the actual risk is unknown. The non-clinical assessment of tanezumab effects on primate pre-and postnatal development included: (1) an enhanced prenatal and postnatal development study (ePPND) and (2) a primate modified embryofetal development study to evaluate tanezumab effects on pre-and post-natal development when given in the first trimester. See the Investigator's Brochure for summaries of these early development studies.

Results from the ePPND study assessing the effects of tanezumab on prenatal and postnatal development when administered weekly by Intravenous (IV) injection to maternal cynomolgous monkeys has shown an increase in total pregnancy loss (sum of embryo-fetal losses and stillbirths) in all treatment groups in comparison to concurrent controls. Gross morphological evaluations of the stillborn animals in this study did not reveal any

observations to suggest a cause of death. The significance of these findings to humans is uncertain at this time.

Strategies have been incorporated into the tanezumab development program to mitigate the risk of pregnancy for women of childbearing potential (WOCBP) and are available in the individual study protocols. Adherence to these requirements will be expected across all ongoing and planned clinical studies with tanezumab.

To assess the safety of infants potentially exposed in-utero to investigational drug due to maternal participation in any ongoing or planned clinical study with tanezumab, this study will evaluate the postpartum neurologic and cognitive development of infants up to the age of 15 months based on neurological examinations and standardized evaluations of cognitive development. The sponsor will attempt to enroll all eligible infants. However, because pregnant women are excluded from tanezumab clinical studies and pregnancies during clinical studies are discouraged, the sponsor does not anticipate a substantial number of potential subjects. Therefore, this study is not intended to generate any formal statistical inferences, but rather to follow-up and characterize the outcomes of all pregnancies to women subjects of childbearing potential (WOCBP) within the clinical program.

Complete information for this compound may be found in the Single Reference Safety Document, which for this study is the Investigator's Brochure (IB). The Single Reference Safety Document for any comparator agent in a parent study is its approved product label.

2. STUDY OBJECTIVES AND ENDPOINTS

2.1. Objectives

This study will examine post-natal neurologic and cognitive development of infants who were exposed to tanezumab or placebo or comparator in-utero during the tanezumab clinical program (through maternal participation in a tanezumab clinical study) within the following protocols: A4091056, A4091057, A4091058, A4091059, A4091061 and A4091063. The specific objective is:

- Evaluate physical development, neurological development (including the autonomic nervous system) and cognitive development through the age of 15 months of infants (and possibly beyond until the infant is considered stable in the judgment of the pediatric neurologist, developmental psychologist or pediatrician) exposed to tanezumab, placebo or comparator in-utero due to maternal participation in a tanezumab clinical study. All observed or volunteered SAEs and non-serious neurological or neuro-developmental adverse events regardless of treatment group or suspected causal relationship to the investigational product(s) will be reported.

2.2. Endpoints

The specific endpoints for this study are:

- Physical/safety measures (occipital-frontal head circumference, length, weight) and vital signs (blood pressure, pulse rate, respiratory rate, temperature).
- Neurological measures (mental status, cranial nerves, motor and sensory systems, reflexes).
- Psychological measures: Bayley Infant Neurodevelopmental Screener (BINS), Bzoch-League Receptive Expressive Emergent Language Test, third edition (REEL-3).

3. STUDY DESIGN

This study is a multicenter, prospective, cohort study with enhanced physical and neurodevelopmental surveillance to characterize the outcomes related to the development of infants up to the age of 15 months, who were exposed to tanezumab, placebo or comparator via maternal exposure at conception or in-utero in any tanezumab clinical study at any investigational site. The postnatal monitoring will include assessments at birth, (0-2 months), approximately 8 months and approximately 15 months of age up to a maximum of 36 months of age as needed.

4. SUBJECT SELECTION

This study can fulfill its objectives only if appropriate subjects are enrolled. The following eligibility criteria are designed to select subjects for whom participation in the study is considered appropriate. All relevant medical and nonmedical conditions should be taken into consideration when deciding whether a particular subject is suitable for this protocol.

Reporting and tracking of exposure in-utero should be performed as outlined in the tanezumab study the parent was participating in and is not within the scope of this protocol. Monitoring of pregnancy outcomes is within the scope of the tanezumab clinical study in which the parent was participating.

Once a pregnancy or maternal exposure has been identified from one of these studies, the female clinical study participant and mother of the infant (the subject), will be invited to enroll her infant in this postnatal monitoring protocol by the investigator. For the child to participate in this study, the mother of the subject must review, agree and sign an informed consent document explaining the details of the postnatal follow-up.

4.1. Inclusion Criteria

Subject eligibility is to be reviewed and documented by an appropriate member of the investigator's study team before subjects are included in the study.

Subjects must meet all of the following inclusion criteria to be eligible for enrollment into the study:

1. Subject is an infant born to a mother who was exposed to study drug on a tanezumab clinical study (tanezumab, placebo or comparator).
2. The infant's mother (who was the tanezumab clinical study participant) must review, agree and sign an informed consent document explaining the details of the perinatal and post-natal follow-up. Where local regulations mandate, the male parent would also review and sign the informed consent.
3. Parent(s) or legal guardian must be willing and able to comply with scheduled visits and study procedures.

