5.1. Allocation to Treatment

Attempts will be made to enroll all cases of EIU irrespective of prior therapy.

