9. DATA ANALYSIS/STATISTICAL METHODS

This study is designed to evaluate neurological and psychological development outcomes among infants with maternal exposure in-utero in tanezumab clinical studies. Because all tanezumab clinical studies exclude women who are currently pregnant and instruct female subjects of childbearing potential and at risk for pregnancy to use highly effective method(s) of contraception throughout the study and for 16 weeks after the last dose of subcutaneous investigational product, the total number of eligible subjects is expected to be small (fewer than 20). As such, there will not be sufficient statistical power to make use of formal statistical comparisons. Therefore, all analyses will be descriptive in nature, primarily through counts of observed outcomes.

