4. ANALYSIS SETS

4.1. Full Analysis Set

The primary analysis set for this study will be the Safety Population, defined as all subjects enrolled into the study. Subjects will be classified according to which treatment the mother was classified as receiving for safety analyses in the original tanezumab clinical study.

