6.6. Safety Summaries and Analyses

Standard safety reporting tables will list the safety data (including Adverse Events and Serious Adverse Events) as well as list patient demographics, disposition and summary status. A non-standard table will be produced listing parental characteristics to include the study, center, patient ID, and treatment group of the mother, and SAE report number associated with the pregnancy. Additional non-standard tables will list the outcome post delivery (newborn length, weight and head circumference) as well as investigator responses on the maturation and development assessment form.

In addition, a listing will be produced to evaluate exposure (days) from conception. The exposure is defined as

- ✓ the date from conception to last dose (injection) + 16 week for tanezumab, and
- ✓ the date from conception to the end of treatment for oral treatment group (tramadol).

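### Neither inclusion criterion 1 nor the Safety Population links maternal dosing to conception, so infants whom SAP 6.6 scores as unexposed still count in the treatment-group rates

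*Protocol*

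**What the plan says.** **Target population.** Protocol Section 2.1 sets out to study "infants who were exposed to tanezumab or placebo or comparator in-utero during the tanezumab clinical program". Section 3 widens this slightly to exposure at conception or in utero. Section 5.1 states the recruitment aim: "Attempts will be made to enroll all cases of EIU irrespective of prior therapy".

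**Eligibility.** Criterion 1 in Section 4.1 reads "Subject is an infant born to a mother who was exposed to study drug on a tanezumab clinical study" and then names tanezumab, placebo or comparator. Criteria 2 and 3 concern consent and willingness to comply. Section 4.2 has no exclusions. Section 4 describes the invitation as following this step: "Once a pregnancy or maternal exposure has been identified from one of these studies".

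**Analysis.** SAP 4.1 has one analysis set, "defined as all subjects enrolled into the study", with each infant classified by the mother's treatment. SAP 6.1 gives counts and rates by treatment arm plus individual narratives. SAP 6.4 plans no subsets.

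**Exposure.** SAP 6.6, extended in version 3.0, adds a listing of exposure days. The tanezumab rule is "the date from conception to last dose (injection) + 16 week for tanezumab". For oral tramadol, exposure runs from conception to the end of treatment. No rule is given for placebo or for any other comparator. The definition feeds the listing only.

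**The concern.** The objective defines the cohort by exposure of the conceptus. The rules that decide who is enrolled and who is counted refer only to exposure of the mother, at any time. Site staff document eligibility against Section 4.1, not against the design paragraph, and the programmer builds denominators from SAP 4.1. Neither text distinguishes an exposed infant from an unexposed one.

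This is a small safety study whose main output is rates by group. If tanezumab has an effect in utero, unexposed infants in the tanezumab denominator would be expected to pull that group's rate down. The same could happen in the comparator group, under a different time rule.

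**Working it through.** **No planning figure to reproduce.** Protocol Section 9.1 calculates no sample size, and the expectation of fewer than 20 infants in Section 9 has no stated derivation. One consistency check is possible. The contraception instruction in Section 9 runs "for 16 weeks after the last dose of subcutaneous investigational product", and 16 × 7 = 112 days, which agrees with the 112 days in Section 14. In neither place is this period an eligibility or analysis-set condition.

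**Step 1: apply SAP 6.6.** Let g be the conception date minus the last dose (tanezumab) or minus the end of treatment (tramadol), in days.

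- Tanezumab exposure = 112 − g
- Tramadol exposure = −g

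| g (days) | Tanezumab | Tramadol |
|---|---|---|
| −28 | 140 | 28 |
| 0 | 112 | 0 |
| 28 | 84 | −28 |
| 84 | 28 | −84 |
| 112 | 0 | −112 |
| 113 | −1 | −113 |
| 180 | −68 | −180 |

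Exposure is zero or negative from g = 112 for tanezumab and from g = 0 for tramadol.

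**Step 2: trace such an infant through the plan.** The mother received study drug, so criterion 1 is met. Nothing excludes the infant (Section 4.2). Once enrolled, the infant is in the Safety Population (SAP 4.1), is counted in the rates of the mother's group (SAP 6.1), and is not separated by any subset (SAP 6.4). The listing in SAP 6.6 would show zero or negative exposure days.

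**Step 3: effect on a rate.** Let n be the infants enrolled in a group, k those with no exposure by SAP 6.6, and x the events. If all events are in exposed infants:

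- all-enrolled rate = x/n
- exposed-only rate = x/(n − k)
- all-enrolled rate = exposed-only rate × (n − k)/n

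The documents give neither n by group nor k, so these values are assumptions, with x = 1:

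| n | k | All enrolled | Exposed only |
|---|---|---|---|
| 5 | 1 | 1/5 = 20.0% | 1/4 = 25.0% |
| 5 | 2 | 1/5 = 20.0% | 1/3 = 33.3% |
| 10 | 1 | 1/10 = 10.0% | 1/9 = 11.1% |
| 10 | 3 | 1/10 = 10.0% | 1/7 = 14.3% |
| 19 | 1 | 1/19 = 5.3% | 1/18 = 5.6% |
| 19 | 3 | 1/19 = 5.3% | 1/16 = 6.3% |

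The rows with n = 19 put every infant in one group, the largest size consistent with fewer than 20. If the single event is instead in an unexposed infant, the shift reverses: with n = 5 and k = 1, 1/5 = 20% becomes 0/4 = 0%.

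**The case against.** The best defence is that the breadth is deliberate and the real gate lies elsewhere. The rationale at the end of Protocol Section 1.2 speaks of potential exposure and of following all pregnancies in the programme, and Section 5 repeats the idea of potential exposure. Wide capture is sensible in surveillance of so few infants. Section 4 leaves the tracking of in-utero exposure to the parent studies, and SAP 6.6 lists an SAE report number tied to the pregnancy. Entry therefore appears to run through parent-study pregnancy reports, which may carry time limits not visible here. The study has no hypotheses or decision rules, and the listing and narratives would show an unexposed infant individually.

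Most of this stands, and it rules out several stronger readings:

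- A reader might infer that any dosed woman can enrol any child, because Section 4 mentions a pregnancy or maternal exposure as alternatives. That reading would make the invitation step meaningless, since every treated woman has maternal exposure, and it sits badly with the aim in Section 5.1.
- A reader might infer that infants conceived a year after dosing, or born before the first dose, will be enrolled. Criterion 1 literally allows both, but the parent studies exclude pregnant women, identification is through those studies, and Visit 1 falls at 0 to 2 months of age. Both cases are improbable.
- A reader might infer that 112 days should become the eligibility limit for every group. That contradicts SAP 6.6. A tramadol infant conceived 84 days after the end of treatment would pass the limit with −84 exposure days.

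What the defence does not answer is the denominator. Broad enrolment calls for an analysis rule on who counts as exposed, and the SAP defines exposure without using it in any rate.

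**Conclusion.** The point holds as a gap between the stated target and the counting rule. By the SAP's own definition, an infant with no in-utero exposure can be eligible and remain in the group rates, with no exposed-only summary beside them.

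Its size is unknown. The count of such infants is not in the documents and is probably low. On the assumed numbers above, one unexposed infant moves a rate by 5 percentage points in a group of five (20% to 25%) and by about 0.3 points in a group of 19. The direction depends on where the events fall.

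A reader might infer that the study is therefore biased toward finding no harm. The documents do not support that as a finding. It would require unexposed infants to be enrolled and the drug to have an effect, and neither is shown. The analysis is descriptive and individual cases are narrated. The point deserves action because the denominators are very small and the remedy is nearly free.

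**What to change.** Keep enrolment broad and keep the all-enrolled summary. In the SAP:

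1. Add to Section 4.1 an exposed-in-utero analysis set: infants with SAP 6.6 exposure greater than zero who were in utero at or after the mother's first dose. The second condition is needed because the SAP 6.6 formula would give an infant born before the first dose a large positive value.
2. Use the treatment-specific rules already in SAP 6.6. Extend them explicitly to placebo and to any other comparator, on the same basis as the matching route, so that the groups stay comparable.
3. Report counts and rates by treatment group for this set alongside all enrolled infants, and list infants outside it separately.

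In the protocol, reconcile the wording of criterion 1 in Section 4.1 with Sections 3 and 5.1. Do not impose a uniform 112-day eligibility limit.

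**Cost.** A few sentences in the SAP, one additional set of summaries and a wording change in the protocol. No new data collection is needed: Section 6.2.1.1 already puts the estimated conception date and last maternal dosing date on the CRF, and other dosing dates belong to the parent studies. The downsides are that conception dates are estimates, so borderline infants may be misclassified, and that the exposed set may be slightly smaller.
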